## Study Objectives

Rise for Health will examine 3-month changes in biomarkers of healthy aging and physical, emotional, and cognitive functioning across a 3-arm randomized trial: (1) healthy living attention control (Healthy Living), (2) reduce sitting time (Reduce Sitting), and (3) increase sit-to-stand transitions (Increase Transitions). The study aims to enroll 405 postmenopausal women into the 3-month trial. The primary aim is to compare changes in glucoregulatory biomarkers (fasting plasma insulin and glucose, HbA1c, and HOMA-IR) and blood pressure over 3 months for the 2 intervention arms compared with the attention control condition. We hypothesize that, compared with those allocated to the attention control arm, participants in the 2 intervention arms will have greater improvements in glycemic control and blood pressure. In addition, we will evaluate the dose-response effects of sitting behavior changes on glucoregulatory biomarkers and blood pressure. We hypothesize that greater improvements in the target behavior will be associated with greater improvements in glucoregulatory biomarkers and blood pressure. The secondary aims of the study are to examine the effects of the intervention on physical, emotional, and cognitive functioning. This project will also explore (1) the modifying effects of age on the relationship between the 3 conditions and primary and secondary outcomes, (2) the psychosocial and mediators and moderators of changes in sitting behaviors, and (3) the differences in outcomes between the 2 sitting interruption intervention arms. The purpose of this paper is to describe the study protocol of Rise for Health, a 3-arm randomized trial, to assess ways of interrupting sitting in postmenopausal women.

The institutional review board of the University California San Diego (UC San Diego) approved all study procedures, and all participants will provide written informed consent. Study recruitment, participant safety, and progress are reviewed semiannually by an external independent data safety monitoring board appointed by the National Institutes of Health (NIH).

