## **Baseline Visit**

Participants return to the clinic after at least seven days of wearing the two devices. Data from activPAL are screened for sitting time (more than 7 hours on a majority of measured days) and sit-to-stand transitions (70 or fewer transitions per day on a majority of measured days) to confirm eligibility. Participants provide fasting blood samples via a finger prick to screen for HbA1c. Those who pass these final eligibility criteria then have a venous blood draw taken by a certified phlebotomist and complete additional questionnaires. Participants receive a total of US \$35 for completing baseline measures. After all baseline assessments are complete, the participants are then randomized.

Randomization is stratified by BMI (overweight vs obese) and employment status (full-time vs nonfull-time employment). A computerized randomization scheme was created using the STAR program grant Biostatistics Core, using a random number generator. A stratified permuted block design is used in this study. After randomization, the participants review the expectations and requirements of their study group assignment (details given in the *3-Month Intervention* section). Data collectors and the principal investigator are blinded to the study group assignment.

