Sedentary Behavior Interrupted:
A Randomized Trial of 3-Month Effects on
Biomarkers of Healthy Aging and Physical
Functioning in the Real World (P2)

NCT03473145

August 26, 2025

Statistical Plan

Baseline characteristics were compared across the 3 treatment arms using ANOVA for continuous variables and χ^2 or Fisher exact tests for categorical variables. Study-related adverse events were tabulated by group using a standard medical dictionary for regulatory activities body system categories.

The primary analysis comparing the sit less and sit-to-stand interventions with the healthy living controls used the intent-to-treat principle. Linear mixed models (LMMs) were applied, allowing for the inclusion of partially complete records, thereby reducing complete case analysis biases. The model included baseline and 3-month outcomes as dependent variable; time (baseline, 3-month), group (active, control), and the group*time interaction were fixed-effect independent (categorical) variables. A subject-specific (random) intercept was included to model individual heterogeneity in outcomes. A significant group*time interaction indicated that outcome changes differed between that intervention and the control arm; this difference of outcome changes between intervention and control arms represents the intervention effect.

To reduce the chance of false positives, we first fit the aforementioned LMMs for 2 primary composite outcomes: (1) glucoregulatory outcomes defined as the average of 4 Z scores of insulin, glucose, HbA1c, and HOMA2-IR; and (2) blood pressure composite defined as the average of 2 Z scores of systolic and diastolic blood pressure. The Z score for each participant for a specific marker and time point was derived by subtracting the sample baseline mean from the participant's marker value at that time point and dividing this difference by the sample baseline SD. This composite score analysis represents an omnibus test of intervention efficacy across multiple (correlated) outcomes: rejection of the null hypothesis would suggest that the intervention (compared with controls) effected changes across components of the composite score. After this composite score analysis, we compared group differences for each of the outcomes; we present intervention results for the individual markers.

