Several secondary analyses were conducted. First, we evaluated intervention effects adjusted for baseline stratification variables (obesity status, employment status). Second, we evaluated group differences in outcomes between the 2 intervention arms. Third, we evaluated changes in physical activity (standing, stepping, light physical activity, and MVPA) by intervention arm. Fourth, we included an indicator variable for COVID-19 (yes or no) and evaluated 3-way COVID-19*group*time interaction (by likelihood ratio tests) to test whether changes in outcomes differed between participants with delayed 3-month assessment because of COVID-19 and those who received the original protocol. Fifth, we explored whether baseline hypertension status was an effect modifier for blood pressure and whether baseline glycemic status (HbA1c < or \geq 5.7%) was an effect modifier for glucoregulatory outcomes. We also excluded participants who self-reported having type 2 diabetes at baseline and repeated the LMM analysis. Last, we examined whether changes in MVPA altered the intervention effect estimates by including MVPA at baseline and 3 months as a time-varying covariate, and the MVPA*group interaction in the LMMs.

Gaussian link functions were used in the mixed models, and diagnostic plots were generated to evaluate model assumptions. Insulin, glucose, and HOMA2-IR were log-transformed to better approximate Gaussian distributions, and results were presented as geometric means with 95% CIs derived from model estimates (β coefficients) at baseline and at 3 months, along with mean (95% CI) within group changes. For the other outcomes, sedentary behavior measures, and blood pressure, mean (95% CI) at baseline and 3 months, as well as mean (95% CI) within-group change derived from model parameters (β coefficients), are presented. Treatment effects were calculated as the mean (95% CI) of the difference (compared with the control group) in absolute changes (for all outcomes) and percent changes (for log-transformed outcomes) from baseline to 3 months.

Analyses were implemented in the R statistical programming language, and LMMs were executed by R package nlme. All hypothesis tests were 2-sided. We used significance level $\alpha=0.025$ for the primary analyses to adjust for multiple comparisons (2 intervention groups versus control). No multiple comparison adjustment was made for secondary analyses.

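### Within each primary composite, Holm's step-down would use the 5% error more efficiently than a fixed 0.025 for both arms; the fixed rule is valid, so this is an optional improvement with costs to disclose

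*SAP*

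**What the plan says.** The SAP's final paragraph gives a level of 0.025 "for the primary analyses to adjust for multiple comparisons (2 intervention groups versus control" and adds that "All hypothesis tests were 2-sided". It names no method and describes no step-down, gatekeeping or other re-use of alpha.

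The comparisons concerned are defined earlier in the SAP: "The primary analysis comparing the sit less and sit-to-stand interventions with the healthy living controls used the intent-to-treat principle". They are made on each of two outcomes, since "we first fit the aforementioned LMMs for 2 primary composite outcomes" (glucoregulatory and blood pressure). That makes 2 × 2 = 4 primary tests. The adjustment named covers the two arms only; none is described across the two composites.

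Effects are reported with 95% intervals: "Treatment effects were calculated as the mean (95% CI) of the difference (compared with the control group) in absolute changes".

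The Protocol (Study Objectives) expects both arms to succeed: compared with the attention control, "participants in the 2 intervention arms will have greater improvements in glycemic control and blood pressure".

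**The concern.** With two hypotheses in a family, Bonferroni tests each at 0.025 whatever happens to the other. Once one arm has been rejected at 0.025, only one null hypothesis can still be falsely rejected. Testing it at 0.025 then uses half of the error that a 5% guarantee allows.

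The Protocol's hypothesis is that both arms beat control, which is where the fixed rule gives up most. A second arm with a p-value between 0.025 and 0.05 is declared negative even though the first arm has already succeeded and a rule with the same per-composite guarantee would have declared it positive.

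**Working it through.** **Inputs from the documents.** Per-test level 0.025 and two-sided tests (SAP, final paragraph); two arms against one control on each of two composites (SAP, primary analysis paragraphs); planned enrolment from the Protocol, Study Objectives: "The study aims to enroll 405 postmenopausal women into the 3-month trial".

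**Assumptions.** The allocation ratio is not given; the Protocol (Baseline Visit) says only that "A stratified permuted block design is used in this study". I assume 1:1:1, so 405/3 = 135 per arm and a correlation of 0.5 between the two test statistics through the shared control. Test statistics are taken as normal. The supplied documents give no power, effect size, SD or dropout, so every power figure below is illustrative.

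**Step 1: reproduce the SAP's figure.** 0.05/2 = 0.025. The SAP states only 0.025; the overall 5% is inferred.

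**Step 2: compare the rules within one composite.** Write p(1) ≤ p(2) for the two arm-versus-control p-values.

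- Fixed rule: reject each arm whose p ≤ 0.025.
- Holm: reject the arm with p(1) if p(1) ≤ 0.025; if so, reject the other if p(2) ≤ 0.05.

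The decisions differ only when p(1) ≤ 0.025 and 0.025 < p(2) ≤ 0.05. Holm then adds the second arm. It never removes a rejection.

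**Step 3: power at an assumed 80% per arm.** Two-sided critical values are 2.241 (0.025) and 1.960 (0.05). The mean of each statistic is 2.241 + 0.842 = 3.083. With 135 per arm this is a standardised difference in change of 3.083 × √(2/135) = 0.375. From the bivariate normal distribution with equal effects:

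- Both arms, fixed rule: 68.7%.
- At least one arm, either rule: 80.0 + 80.0 − 68.7 = 91.3%.
- Probability of the region where the rules differ: 9.1%.
- Both arms, Holm: 68.7 + 9.1 = 77.8%.
- Per arm, Holm: 80.0 + 9.1/2 ≈ 84.6%.

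| Assumed scenario | Per arm, fixed → Holm | Both arms, fixed → Holm |
|---|---|---|
| Equal effects, 50% power | 50.0% → 55.2% | 33.3% → 43.7% |
| Equal effects, 60% power | 60.0% → 65.5% | 43.9% → 54.8% |
| Equal effects, 80% power | 80.0% → 84.6% | 68.7% → 77.8% |
| Equal effects, 90% power | 90.0% → 93.1% | 83.2% → 89.4% |
| Standardised difference 0.35, 135 per arm | 73.7% → 78.8% | 60.4% → 70.5% |
| Standardised difference 0.35, 108 per arm (20% loss) | 63.0% → 68.4% | 47.3% → 58.2% |

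If the second arm has half the effect (first arm at 80% power), the chance of declaring both goes from 23% to 32%. If only one arm works, its own power hardly moves (80.0% to 80.2%).

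**Step 4: error within one composite.**

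- Both arms null: 4.65% under either rule.
- One arm null: the fixed rule gives 2.5%. Holm gives 4.2% when the other arm has 80% power, and at most 5.0% as that power approaches 100%.

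**Step 5: error across all four primary tests.** The bound is 4 × 0.025 = 10% for the fixed rule and 2 × 0.05 = 10% for Holm within each composite. Simulation with 2 million draws, for an assumed correlation between composites of 0.6 to 0:

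| Truth | Fixed 0.025 | Holm within composite |
|---|---|---|
| No effect anywhere | 8.3–9.0% | 8.3–9.0% |
| One arm works on both composites at 80% power, the other on neither | 4.5–4.9% | 7.5–8.3% |
| The same, with a very large effect in the working arm | 4.5–5.0% | 8.8–9.8% |

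**The case against.** The strongest case for leaving the rule alone has four parts.

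1. **Nothing is wrong with it.** Bonferroni at 0.025 is valid for the pair, transparent and conventional. This stands. A reader might infer from the power figures that the SAP contains an error; it does not. The loss is one of efficiency, and only for the second rejection.

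2. **Holm is not free across the trial.** A reader might also infer that Holm leaves the trial's overall error unchanged at 5%. The documents do not support that: the SAP runs four primary tests and adjusts only for the two arms. When one arm is null on both composites, the fixed rule happens to stay below 5% trial-wide and Holm within composites does not (Step 5). A sponsor could prefer the fixed level for that reason. The cost is real and must be stated, but it is not decisive. The fixed rule already reaches 8.3–9.0% when nothing works, both rules share the 10% bound, and the SAP claims no control over that wider family.

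3. **It may be too late.** The SAP is dated August 26, 2025 and describes its analyses as done. Holm can only add rejections, so adopting it after results are known would relax the success criterion. It would also make the SAP misdescribe the rule that was used. This stands in full and governs how the fix must be applied.

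4. **Bonferroni comes with simple matching intervals.** In general that is an advantage, since 97.5% intervals agree with tests at 0.025. It carries little weight here, because the SAP reports 95% intervals and there are no 97.5% intervals to retain.

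**Conclusion.** The point holds as one of efficiency within a single composite. Holm on the same two p-values keeps the per-composite familywise error at or below 5% under any dependence and never rejects less than the fixed rule. With equal effects and starting powers of 50% to 90%, the gain is about 3 to 5.5 points per arm and 6 to 11 points for declaring both. The size rests on assumed 1:1:1 allocation, normal statistics and an assumed starting power. The actual gain in this trial is unknown, and it is nil unless one arm has p ≤ 0.025 and the other falls between 0.025 and 0.05.

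The point does not extend to the choice of primary family, and Holm within composites does not supply the missing adjustment across them. I regard it as a cheap, optional improvement of low priority.

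**What to change.** If the primary results are not yet known, replace the fixed level in the SAP's final paragraph with:

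*Within each primary composite, the smaller of the two arm-versus-control p-values is tested at 0.025; if significant, the larger is tested at 0.05 (Holm).*

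Report Holm-adjusted p-values, 2 × p(1) for the smaller (capped at 1) and the larger of 2 × p(1) and p(2) for the other, each compared with 0.05. Place them next to the 95% intervals already planned and note that the decision follows the adjusted p-value. The note is needed because a 95% interval can exclude zero when p(1) lies between 0.025 and 0.05 and nothing is rejected.

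If the results are known, leave the stated rule as it is. Report the fixed-0.025 decisions as primary and the Holm decisions beside them as a labelled post hoc supplement.

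In either case, state two costs: the false-positive rate for a truly null second arm rises from 2.5% to at most 5% per composite, and control is per composite, with a bound of 10% over the four primary tests. A sponsor who wants 5% trial-wide would need Holm over all four p-values or another rule across composites, which is a different family from the one the SAP names.

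No new data or models are needed. The work is one sentence, two adjusted p-values per composite and the disclosure. Keeping the fixed rule with a sentence explaining the preference would also be acceptable.
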